#### **4.2.3.2 Subjects whose height measurement at visit 7 (week 52) was performed later than planned**

Additional sensitivity analysis of primary endpoint using single imputation will be performed to investigate the impact of delayed visit on height velocity after 52 weeks of treatment. The single imputation will be done by making a linear interpolation between that last observed height prior to week 52, meaning the visit 6 (week 39) height measurement, and the observed delayed visit 7 height measurement. From this linear interpolation we find the height at week 52 and calculate a week 52 HV and data will be analysed using the same analysis model as was used for analysing the primary endpoint for the primary estimand. From this analysis an estimate of the treatment difference at week 52 with corresponding 95% CI will be presented.

#### **4.2.3.3 Adjusting for baseline IGF-I SDS**

As an additional sensitivity analysis the primary endpoint for the primary estimand will also be analysed adding baseline IGF-I SDS as a covariate in the primary analysis model. From this analysis an estimate of the treatment difference at week 52 with corresponding 95% CI will be presented

### **4.2.4 Supplementary Analysis**

An analysis of the primary endpoint using the same analysis model as was used for the primary analysis under the primary estimand but based on PP instead of FAS will be conducted as a supplementary analysis.

## **4.3 Secondary Endpoints Analysis**

### **4.3.1 Confirmatory Secondary Endpoints**

Not applicable

### 4.3.2 Supportive Secondary Endpoints

#### Table Efficacy

Endpoint title	Time frame	Unit
Change in bone age	From visit 1 to week 52	Years
Change in Height Standard Deviation Score	From baseline (week 0) to week 52	-10 to +10
Change in Height Velocity Standard Deviation Score	From baseline (week 0) to week 52	-10 to +10

The efficacy endpoints will be analysed based on the 'on-treatment' observation period as well as the 'in-trial' observation period within the trial period (52 weeks of treatment).

Height SDS will be derived using Chinese general population standards and HV SDS will be derived using Prader standards as reference data.

The formula to calculate height SDS is as below:

$$\text{Height SDS} = ((\text{Height} / M)^{\text{L-1}}) / (\text{L} * \text{S})$$

Height: height at the time of assessment,

L: The sex and age-specific power in the Box-Cox transformation,

M: The sex and age-specific median,

S: The sex and age-specific generalized coefficient of variation

The Chinese standards data contained three heights in cm corresponding to the median and plus/minus 2 SD for ages 0 to 18 years every six month, separately for girls and boys. Using these data as input, LMS values were calculated using the LMSfit function in R4.2.0 at these ages.

With the calculated LMS values as input the smooth.spline function with degrees of freedom 10 for L, 15 for M and 25 for S was used to obtain smoothed monthly estimates of LMS, separately for girls and boys. Finally, height SDS was calculated using above formula based on the smoothed monthly estimates.

Change in height SDS and HV SDS will be analysed using the same analysis model as was used for analysing the primary endpoint for the primary estimand except for using baseline height SDS and baseline HV SDS, respectively, as a covariate in the model instead of baseline height. The estimate for the treatment difference at week 52 will be reported with corresponding 95% CI and p-value.

Bone age will be analysed using an ANCOVA model on bone age/chronological age assessed at week 52 and the model will include treatment, sex, age group, GH peak group and sex by age group

interaction term as factors and baseline bone age/chronological age as a covariate. The treatment difference estimate will be reported with corresponding 95% CI and p-value.

### Table Safety

Endpoint title	Time frame	Unit
Change in fasting plasma glucose	From baseline (week 0) to week 52	mmol/l
Change in HbA1c	From baseline (week 0) to week 52	%

The safety endpoints will be analysed using descriptive statistics based on the 'on -treatment' observation period and the 'in-trial' observation period.

### Table Pharmacodynamics

Endpoint title	Time frame	Unit
Change in IGF-I Standard Deviation Score	From baseline (week 0) to week 52	-10 to +10
Change in IGFBP-3 Standard Deviation Score	From baseline (week 0) to week 52	-10 to +10

The PD endpoints will be analysed based on the 'on -treatment' observation period and the 'in-trial' observation period.

Change in IGF-I SDS and IGFBP-3 SDS will be analysed using an MMRM with an unstructured covariance matrix on all relevant post-baseline change from baseline values as dependant variables. The model will include treatment, sex, age group, region, GH peak group and sex by age group interaction term as factors and baseline value as a covariate, all nested within week as a factor. From the MMRM, the treatment difference at week 52 will be estimated and the corresponding 95% CI and p-value will be reported for each endpoint.

#### 4.4 Exploratory Endpoints Analysis

Not applicable

## 4.5 Other Safety Analysis

The subsections refer to analysis of other safety parameters. For calculation of derived safety parameters please see appendix 1, section [6.1](#).

### 4.5.1 Extent of Exposure

Not applicable

### 4.5.2 Adverse Events

Adverse events will be analysed using descriptive statistics based on the ‘on –treatment’ observation period (primary evaluation) and ‘in-trial’ observation period (secondary evaluation) within the main trial period (52 weeks of treatment). The adverse events will be summarised by treatment, MedDRA (Medical Dictionary for Regulatory Activities) system organ class and MedDRA preferred term. The descriptive statistics will include the number and percentage of subjects who experienced adverse events, the number of events and rate. Adverse events will be listed by treatment and subject with information on severity, relationship to trial product and demographics based on the ‘on –treatment’ observation period. Adverse events with onset 14 days or more after last trial drug administration will be reported in a separate listing. Adverse events with onset before first dosing will be reported in a separate listing.

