#### Overall design:

A randomised open-labelled two arm trial designed to confirm non-inferiority of efficacy and investigate safety of once weekly subcutaneous treatment of somapacitan compared to daily subcutaneous growth hormone (Norditropin®) treatment in Chinese prepubertal children with growth hormone deficiency.

The total trial duration for a subject will be 58 to 70 weeks approximately.  
The trial duration includes a 2 to 14 weeks screening period, a 52 weeks treatment period and a minimum of 30 days follow up period.

Eligible subjects will be randomised in a 2:1 manner to receive either somapacitan or Norditropin®. A non-inferiority margin of -2.0 cm/year is used in the trial. The randomisation will be stratified by age (<6 versus  $\geq 6$  years), gender (boys versus girls) and GH peak (< 7 versus  $\geq 7$  ng/ml) ensure equal distribution of these factor levels across treatment.

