## **7.1 Discontinuation of trial treatment**

A subject who does not fulfil the eligibility criteria (inclusion/exclusion criteria) must not be randomised. Randomisation in violation of any of the eligibility criteria is a Good Clinical Practice (GCP) non-compliance and must be reported to the sponsor without delay. This will be handled as an important protocol deviation, and the independent ethics committee (IEC)/ institutional review board (IRB) and regulatory authorities must be notified according to local requirements. If there are no safety concerns, trial treatment may be continued or resumed at the discretion of the investigator after agreement with the sponsor's global medical expert.

The trial product must be discontinued, if any of the following applies for the subject:

1. Safety concern related to trial product or unacceptable intolerance
2. Simultaneous use of an approved or non-approved investigational medicinal product in another clinical trial
3. Tumour development

See the flowchart [1.2](#) for data to be collected at the time of treatment discontinuation (early discontinuation visit) and follow-up and for any further evaluations that need to be completed.

The purpose of the follow-up visit is to collect information about adverse events. For convenience of the subject the follow up visit can be performed as a telephone contact. The follow up visit should be performed as a site visit for subjects with an ongoing injection site reaction at visit 8.

The primary reason for discontinuation of trial product must be specified in the end-of-treatment-form in the CRF, and final drug accountability must be performed. A treatment discontinuation session must be made in the IWRS.

If a subject discontinues treatment prior to visit 7, Visit 7A should be performed at least 7 days after the last dose of trial product and prior to starting treatment with marketed product. The follow up visit should be performed 30 days after the last dose of trial product.

Although the treatment has been discontinued, the subject will continue to follow the planned visit schedule until visit 7 (52 weeks).

If the subject or family refuse to attend planned visit schedule, then efforts should be made for the subject to attend visit 7 as it is the primary endpoint visit.

After visit 7A the following assessments are not applicable for subjects who discontinue trial product:

- Trial drug administration
- Drug accountability
- PK and Antibody sampling

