#### **9.4.4      Other safety analyse(s)**

All safety analyses will be made on the safety analysis set. The standard safety assessments (AEs, safety laboratory parameters, vital signs, etc.) will be analysed using descriptive statistics based on the ‘on –treatment’ observation period. Additionally, AEs will also be analysed using descriptive statistics based on the ‘in-trial’ observation period.

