### 3 Analysis Sets

The following populations are defined:

Population	Description
Full analysis set (FAS)	All subjects randomised. Exclusion of data from analyses should be used restrictively, and normally no data should be excluded from the FAS. Subjects will be analysed according to the randomised treatment
Safety analysis set (SAS)	All subjects randomly assigned to trial treatment and who take at least 1 dose of trial product. Subjects are analysed according to the treatment they actually received.
Per protocol analysis set (PP)	Subjects from FAS who have not violated any inclusion/exclusion criteria and have used the randomised treatment for at least 47 weeks (for subjects receiving somapacitan) or 329 days (for subjects receiving Norditropin) corresponding to 90% of the planned exposure. Subjects are analysed according to the treatment they actually received.

The subjects or observations to be excluded, and the reasons for their exclusion must be documented before unblinding. The subjects and observations excluded from analysis sets, and the reason for this, will be described in the CTR. Two observation periods are defined:

- on-treatment: from first administration and up until last trial contact, visit 7 or 14 days after last administration, whichever comes first
- in-trial: from first administration and up until last trial contact or visit 8, whichever comes first

Analysis based on the 'in-trial' observation period is to be viewed as supplemental analysis to the analysis based on the 'on-treatment' analysis.

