#### **4.8 Changes to Protocol-planned Analysis**

There are no changes to the protocol-planned analysis.

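### SAP 4.5.2 confines the adverse-event summaries to an undefined 52-week period, so for on-schedule completers the in-trial table omits the safety follow-up to visit 8

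*SAP*

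**What the plan says.** - **Period definitions.** SAP 3, repeating Protocol 9.3, defines two windows: "on-treatment: from first administration and up until last trial contact, visit 7 or 14 days after last administration, whichever comes first" and "in-trial: from first administration and up until last trial contact or visit 8, whichever comes first".
- **Protocol plan for AEs.** Protocol 9.4.4 bases the standard safety analyses on the on-treatment period, then says "Additionally, AEs will also be analysed using descriptive statistics based on the" in-trial period. It sets no 52-week limit.
- **SAP plan for AEs.** SAP 4.5.2 makes on-treatment the primary evaluation, followed by the in-trial "observation period (secondary evaluation) within the main trial period (52 weeks of treatment". The clause can be read as applying to both summaries.
- **AE listings.** The same SAP section lists AEs for the on-treatment period. It puts those with onset 14 days or more after the last dose in a separate listing, and those before first dosing in another.
- **Follow-up.** The protocol synopsis counts "a 52 weeks treatment period and a minimum of 30 days follow up period" as separate components. Protocol 7.1 says of visit 8: "The purpose of the follow-up visit is to collect information about adverse events". Protocol 8.3.1 has AEs collected until that visit.
- **Declared changes.** SAP 4.8 states: "There are no changes to the protocol-planned analysis".

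**The concern.** An in-trial table normally exists to show events that the on-treatment table leaves out. Here the definition in SAP 3 reaches visit 8, but the analysis text in SAP 4.5.2 stops at 52 weeks of treatment. A programmer who follows SAP 4.5.2 would cut off the follow-up that visit 8 was scheduled to cover. The in-trial table would then not show what its name and definition promise.

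Comparing safety is the trial's secondary objective, and AEs are compared by descriptive tables without a test. What is at stake is whether AEs from completers' post-treatment follow-up enter any of those tables. The added limit is also a departure from Protocol 9.4.4 that the SAP does not declare.

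**Working it through.** **1. Does 52 weeks of treatment include follow-up?** The synopsis gives a total duration of about 58 to 70 weeks. Screening + treatment + follow-up is 2 + 52 + 30/7 = 58.3 weeks and 14 + 52 + 30/7 = 70.3 weeks. The stated total is reproduced only when the 30 days are added to the 52 weeks, so follow-up lies outside them.

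**2. Inputs for a completer (first dose = day 0).**
- Visit 7: 52 weeks + 5 days, ±1 day, so day 368 to 370 (flowchart).
- Somapacitan: visit 7 falls 4 to 6 days after dosing (Protocol Table 15).
- Visit 8: 30 days, +5 (flowchart). Protocol 7.1 counts from the last dose for early discontinuers. The starting point for completers is not stated, so I computed it from the last dose and from visit 7.

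**3. Windows for a somapacitan completer with last dose on day 364 and visit 7 on day 369.**

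| Window | Ends on day |
|---|---|
| On-treatment (SAP 3) | min(369, 364 + 14) = 369 |
| In-trial with the limit, read as visit 7 | 369 |
| In-trial with the limit, read literally | 52 × 7 = 364 |
| In-trial as defined (visit 8) | 394 to 404 |

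The limited in-trial window equals the on-treatment window or is 5 days shorter. The Norditropin arm gives the same ordering.

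**4. Follow-up left out per completer.**
- Limit read as visit 7: visit 8 − visit 7. The smallest value is 393 − 370 = 23 days (Norditropin, last dose day 363). The largest is 30 + 5 = 35 days.
- Limit read literally, last dose day 364: 394 − 364 = 30 days to 405 − 364 = 41 days. If the last dose falls on day 362, the lower end is 392 − 364 = 28.

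**5. Events affected.** Completers: 0.9 × 108 = 97.2, about 97, using the 10% loss assumed in Protocol 9.2. The documents give no AE rate, so I assume 1 to 4 per patient-year. Events = 97 × rate × days / 365.25.
- Visit 7 reading: 97 × 1 × 23 / 365.25 = 6.1 to 97 × 4 × 35 / 365.25 = 37.2.
- Literal reading: 97 × 1 × 30 / 365.25 = 8.0 to 97 × 4 × 41 / 365.25 = 43.6.

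**6. Do the listings cover the gap?** The on-treatment listing ends at visit 7 and the late listing starts at last dose + 14. In the example the gap is 378 − 369 = 9 days. Over the allowed schedules it is 8 to 10 days for somapacitan and 7 to 14 for Norditropin. An AE starting in those days is in neither a summary nor a listing specified in SAP 4.5.2.

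**7. Early discontinuers.** With a last dose on day 140 and visits continued, on-treatment ends on day 154 and the limited in-trial window on day 364 or 369. In-trial still adds 210 to 215 days for such a child.

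**The case against.** The strongest reply is that the clause is leftover labelling. The term main trial period appears nowhere else. SAP 4.5.2 invokes the in-trial period by name, and SAP 3 defines it to visit 8, so a programmer might simply follow SAP 3. In addition, Protocol 9.4.3.2 and SAP 4.3.2 use almost the same clause for the efficacy endpoints. There it must include the week-52 visit, which is scheduled 5 days after week 52. A hard stop at day 364 is therefore the less natural reading. This stands, and it is why the visit 7 figures come first here. It does not remove the conflict, because ending at visit 7 still leaves out the whole of completers' follow-up.

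It is also fair to say that the primary AE evaluation, on-treatment, is untouched if the limit means visit 7. The in-trial table is supplemental. If visit 7 came more than 14 days after the last dose, an in-trial window ending at visit 7 would be longer than on-treatment.

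A reader might infer more than the documents support:
- **That follow-up AEs go unreported.** They do not all go unreported. An AE on day 385, 21 days after a day-364 dose, is in the late-onset listing. It is missing only from the tables.
- **That in-trial rates are 8% to 10% too low.** This needs a numerator cut at day 364 and a denominator running to visit 8. The SAP does not state the denominator.
- **That a late visit 7 costs on-treatment AEs.** This needs the literal reading and dosing beyond week 52. SAP 4.2.3.2 speaks only of a late height measurement.

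**Conclusion.** The point holds as a conflict between SAP 4.5.2 on one side and SAP 3, Protocol 9.3 and Protocol 9.4.4 on the other. Followed as written, the in-trial AE summary adds nothing for on-schedule completers and omits about 23 to 35 days of each child's safety follow-up, or 30 to 41 days on the literal reading. That corresponds to roughly 6 to 37 AEs (8 to 44) outside every table of counts, percentages or rates.

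The day ranges rest on the flowchart windows and on both possible starting points for visit 8. The literal range also assumes a last dose on day 364. The event counts rest on about 97 completers and an assumed rate of 1 to 4 AEs per patient-year, and they move in proportion to that rate. The conflict itself depends on none of these assumptions. The documents do not support a claim that the rates are biased by a known amount or that the comparison between arms is distorted.

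**What to change.** In SAP 4.5.2, delete the clause that confines the summaries to 52 weeks. State that AEs are summarised over the full on-treatment and in-trial periods defined in SAP 3, with in-trial running to visit 8 or last contact. State that each rate is divided by time in the same period. If the sponsor wants to keep the limit, it should define the term, declare the change in SAP 4.8, and add a tabulated summary of AEs from visit 7 to visit 8.

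The cost is one SAP sentence and a different date cut-off in the AE tables. No new data are needed and the primary analysis is unaffected. In-trial AE counts may rise slightly. The deletion restores Protocol 9.4.4 and removes this undeclared departure. It does not by itself make SAP 4.8 accurate, because the sensitivity analyses in SAP 4.2.3.2 and 4.2.3.3 are also absent from the protocol.

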### **Time of injection of Norditropin®**

- Subjects randomised to Norditropin® should inject subcutaneous daily in the evening (to reflect standard treatment practice) throughout the trial.
- Injections with Norditropin® the night before blood sampling for anti-hGH antibodies must occur at least 12 hours prior to planned blood sampling.
- If a subject randomised to Norditropin® forgets or is unable to inject the dose in the evening, the dose should be skipped. The subject should take the next dose on the following evening as scheduled.

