**For subjects randomised to somapacitan:**

**Table 15      Timing of visits and blood sampling**

Visit	Timing of visit
3	1 to 4 days after dosing
4	On a planned dosing day
5	1 to 4 days after dosing
6	On a planned dosing day
7	4 to 6 days after dosing
8	No blood sampling

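### Adverse events that start after visit 7 but less than 14 days after the last dose fall outside the on-treatment summary and all three planned AE listings

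*SAP*

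**What the plan says.** SAP 3 (Analysis Sets) defines two observation periods: "on-treatment: from first administration and up until last trial contact, visit 7 or 14 days after last administration, whichever comes first", and "in-trial: from first administration and up until last trial contact or visit 8, whichever comes first".

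SAP 4.5.2 makes the on-treatment AE summary the primary evaluation and the in-trial summary the secondary one. It then plans three listings:

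- on-treatment events, by treatment and subject, with severity, relationship to trial product and demographics;
- late events: "Adverse events with onset 14 days or more after last trial drug administration will be reported in a separate listing";
- events with onset before first dosing.

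The same section attaches a time limit to the summaries: "observation period (secondary evaluation) within the main trial period (52 weeks of treatment". Protocol 9.4.4 has no such limit: "Additionally, AEs will also be analysed using descriptive statistics based on the ‘in-trial’ observation period". SAP 4.8 reports no change from the protocol-planned analysis.

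On timing, Protocol Appendix 2, Table 15 places visit 7 "4 to 6 days after dosing" for somapacitan. Norditropin subjects "should inject subcutaneous daily in the evening (to reflect standard treatment practice) throughout the trial". AE collection continues to the follow-up visit (Protocol 8.3.1), and Protocol 7.1 states: "The purpose of the follow-up visit is to collect information about adverse events".

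**The concern.** The on-treatment period can be cut short by visit 7, but the post-treatment listing starts a fixed 14 days after the last dose. The two boundaries meet only when on-treatment ends at day 14. That is the usual case for a child who stops trial product early, but not for a completer, so for most of the trial a stretch of collected follow-up belongs to no listing.

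Comparing safety is the trial's only secondary objective, and the follow-up visit exists to collect adverse events. The listing is where SAP 4.5.2 shows severity and relationship to trial product child by child. Events in the gap start within 14 days of the last dose, yet they have no planned subject-level display.

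**Working it through.** **Inputs**

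- End of on-treatment, end of in-trial: SAP 3.
- Listing boundaries: SAP 4.5.2.
- Visit 7: 52 weeks + 5 days, window ±1 day (Protocol 1.2, flowchart); 4 to 6 days after dosing for somapacitan (Table 15).
- Visit 8: 30 days, window +5 (flowchart). Protocol 7.1 counts the 30 days from the last dose for early discontinuation. Both possible starting points are used below.
- 108 randomised 2:1, 10% without usable week 52 data (Protocol 9.2).

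**Step 1: check the stated visit 7 timing.** 5 − 1, 5 and 5 + 1 days after a week 52 dose give 4, 5 and 6 days, which agrees with Table 15.

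**Step 2: classify each onset day, counted from the last dose.** On-treatment if day ≤ min(visit 7, 14); late listing if day ≥ 14; otherwise unlisted.

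| Case | Visit 7 (days after last dose) | Unlisted onset dates | Whole dates | Elapsed days (14 − visit 7) |
|---|---|---|---|---|
| Somapacitan | 4 | 5 to 13 | 9 | 10 |
| Somapacitan | 5 | 6 to 13 | 8 | 9 |
| Somapacitan | 6 | 7 to 13 | 7 | 8 |
| Norditropin (assumed) | 1 | 2 to 13 | 12 | 13 |
| Norditropin (assumed) | 0 | 1 to 13 | 13 | 14 |
| Early discontinuation, on-treatment ends at day 14 | not reached | none | 0 | 0 |

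In the last case day 14 itself falls in both listings. The documents do not fix the last Norditropin dose relative to visit 7. The rows above assume that daily dosing continues to 0 to 1 day before the visit. If the last dose were 4 to 6 days before, the Norditropin gap would also be 8 to 10 elapsed days. All unlisted dates lie before visit 8, so they are inside the in-trial period as SAP 3 defines it.

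**Step 3: share of the time from visit 7 to visit 8 (somapacitan).**

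- Visit 8 at 30 to 35 days after the last dose: 8/29 = 28%, 8/24 = 33%, 10/31 = 32%, 10/26 = 38%.
- Visit 8 at 30 to 35 days after visit 7: 8/35 = 23% to 10/30 = 33%.

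**Step 4: total.** Completers: 72 × 0.9 ≈ 65 and 36 × 0.9 ≈ 32.

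- Somapacitan: 65 × 8 = 520 to 65 × 10 = 650 child-days.
- Both arms: 520 + 32 × 8 = 776 to 650 + 32 × 14 = 1,098 child-days (2.1 to 3.0 child-years).
- By whole dates: 65 × 7 + 32 × 7 = 679 to 65 × 9 + 32 × 13 = 1,001.

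**Step 5: the 52-week phrase.** 52 × 7 = day 364; nominal visit 7 is 364 + 5 = day 369. A literal 52-week cut would end before visit 7, against both period definitions in SAP 3, and would also remove the gap events from the in-trial summary.

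**The case against.** The strongest reply is that these events are still reported. SAP 3 runs the in-trial period to visit 8, and SAP 4.5.2 summarises in-trial events by arm, system organ class and preferred term, with numbers of subjects, events and rates. Severity and causality are recorded for every event, and serious events are reported within 24 hours whatever the observation period. On this view only a line listing is missing. This stands, and it limits the harm. It does not supply the missing listing.

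Second, the literal 52-week reading contradicts SAP 3 and is probably not intended. Near-identical words accompany the efficacy endpoints in Protocol 9.4.3.2 and SAP 4.3.2, so they may have been carried over. That is fair: the phrase is ambiguous, and it does not prove that events drop out. It still conflicts with the in-trial definition and should be settled.

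Third, the size can look inflated. Against on-treatment follow-up of about 97 × 369 = 35,793 child-days, 776 to 1,098 is about 2% to 3%. Whole-date counts are lower, the Norditropin figure rests on an assumption, and child-days are not events; the documents give no AE rate. All of this is correct.

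Fourth, children should move to a marketed product after trial product stops (Protocol 6.7), so some events may arise on another growth hormone. That supports keeping them out of the on-treatment listing, but it does not justify having no listing for them.

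**Conclusion.** The concern holds. For completers on the planned schedule, events that start after visit 7 and before day 14 after the last dose are outside the primary AE summary and every planned listing. No other section closes the gap.

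The size is 8 to 10 elapsed days (7 to 9 whole dates) per somapacitan completer. For Norditropin it is 13 to 14 elapsed days if dosing runs to 0 to 1 day before visit 7. The total assumes 65 and 32 completers. The gap closes only for a child whose visit 7 falls 14 days or more after the last dose.

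The consequence is incomplete descriptive safety reporting. On-treatment follow-up runs to visit 7 in both arms, so no between-arm bias is shown, and the primary analysis is not affected. The point should be corrected, but it does not threaten the trial's main conclusion.

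**What to change.** Keep the on-treatment definition and make two edits in SAP 4.5.2.

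1. Define the post-treatment listing as all adverse events with onset after the end of the on-treatment observation period. It then complements the on-treatment listing exactly: no onset day after first dosing is left out, in either arm, for completers or discontinuers, and the double listing of day 14 disappears.
2. Delete the 52-week phrase from the in-trial AE evaluation, so that it runs to last trial contact or visit 8, as in SAP 3 and Protocol 9.4.4.

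The cost is the two wording changes and one date condition in the AE listing program; the data are already collected. The drawback is a longer post-treatment listing, which will include events that start after a child has moved to a marketed growth hormone product.
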